4.2.2 Masking

Visually, TTHX1114(NM141) is indistinguishable from vehicle, therefore, the clinician administering the intracameral injection will be masked to study treatment assignment. All study subjects will also be masked to study treatment assignment and masked examiners will perform all ocular examinations, including specular microscopy, slit lamp biomicroscopy, dilated eye exam, intraocular pressure (IOP), and BCVA.

4.2.4 Masked Medical Monitor

As described above, the study will include a masked and an unmasked Medical Monitor. To avoid bias on the part of the unmasked Medical Monitor, all communication with the investigational site staff will be through the masked Medical Monitor.

4.3 Study Treatment

Study treatment (TTHX1114(NM141) [1 ng, 3 ng, and 10 ng] or vehicle/ placebo) will be administered as an intracameral injection on Day 0, Day 7, Day 14, and Day 21. Please refer to Section 6.2 for instructions for study treatment administration. Please refer to the Pharmacy Manual for study treatment storage, handling, and preparation instructions.

4.3.1 TTHX1114(NM141) Drug Product

TTHX1114(NM141) drug product is a solution formulated in phosphate buffered saline manufactured in a contract sterile fill/finish facility in compliance with cGMP regulations. TTHX1114(NM141) will be provided in the following concentrations:

Vehicle is the phosphate buffered saline without active ingredient. Study treatment is supplied in 2 mL sterile, plastic, single-use, snap-cap vials with 1 mL of test article in each vial.

4.3.2 TTHX1114(NM141)/ Vehicle Packaging

The study treatment kit will contain 5 vials of masked study treatment vials (1 for each of the 4 study treatment administrations and 1 back-up vial).

Trefoil Therapeutics, Inc.	Clinical Study Protocol TTHX-001
Confidential and Proprietary	Amendment 1.0: September 8, 2020

4.3.3 TTHX1114(NM141)/ Vehicle Storage

The vials are shipped frozen and must be stored **secure** in a secure area. Excursions from temperature limits must be reported to the Trefoil (or designee) to determine whether the affected vials can be used. Access to investigational product must be limited to individuals authorized by the Investigator to dispense the study treatment.

4.3.4 TTHX1114(NM141)/ Vehicle Preparation

Vials must be thawed prior to study treatment administration and gently mixed by inversion. Thawed vials are stable at room temperature for up to 8 hours. Study treatment preparation should be started (i.e.; allowed to thaw at room temperature NB: do not apply external heat) after the subject has arrived in the clinic to undergo study treatment. All study treatment injections must be administered within 8 hours of the start of thawing of the study treatment vial.

Trefoil will supply a low-volume syringe for each study treatment administration.

4.4 Duration of the Study and Study Treatment

Each subject is expected to be on study for approximately 90 days following a 28-day screening period. Study treatment will be administered on Day 0, Day 7, Day 14, and Day 21 as an intracameral injection. Following the last intracameral injection on Day 21, all participants will return to the clinic on Day 28, Day 56 and Day 90 for follow-up assessments.

Figure 2: Study Participant Schema

					St	udy Day		
	0	3	7	14	21	28	56	90
Screening Period (28 days)	-	Study Treatment Period (28 days)					Follow-Up (62 day	
Randomization \blacklozenge								
Study Treatment Administration	♠		♠	1	1			
Efficacy Assessments	Х		х	Х	Х	Х	X*	Х
Safety Assessments	Х	Х	Х	Х	Х	Х	Х	Х

Not to scale.

See Appendix A for a complete schedule of assessments

* Primary efficacy endpoint assessment

4.4.1 Retreatment Criteria

Subject may continue to receive study treatment (Days 7, 14, and 21) as long as they remain eligible and have not experienced any dose limiting toxicity (DLT) (see Section 4.5.1) below.

4.5 Dose Escalation/ Cohort Review

The unmasked Medical Monitor will review all available clinical data when the last subject of the first cohort of subjects completes the Day 7 examinations before enrollment in the second cohort may start. Then, the unmasked Medical Monitor will review clinical data when the last subject in the second cohort completes the Day 7 examinations before enrollment into the third

Trefoil Therapeutics, Inc.	Clinical Study Protocol TTHX-001
Confidential and Proprietary	Amendment 1.0: September 8, 2020

cohort may start. If, at any time, the safety profile is deemed unacceptable, treatment will revert to the prior lower-dose level which was deemed safe.

4.5.1 **Dose Limiting Toxicities**

Potential dose limiting toxicity (DLT) is defined as any of the following events:

- Visual acuity loss of 15 ETDRS letters or more
- > 5 anterior chamber cells observed on slit lamp examination
- > 10 vitreous cells observed on slit lamp examination
- >710 micron corneal thickness or a 150 micron increase from baseline (Day 0 pretreatment)
- Increase of 2 or more grades in conjunctival hyperemia
 - Grade 0 = No vasodilation (Absent)
 - \circ Grade 1 = Some vasodilation
 - Grade 2 = Extensive vessel vasodilation
 - Grade 3 = Overall vasodilation
- IOP that remains higher than 32 mmHg and not responding to therapy

If any subject experiences any of the events listed above, study treatment must be held for at least 7 days, and the masked Medical Monitor must be contacted to discuss medical management of the subject including possible treatment and additional unscheduled study assessments.

After the 7-day study treatment delay, the subject may receive additional study treatment if the subject remains eligible and all of the potential DLTs the subject experienced have decreased to a level that no longer meets the DLT requirements. Any of the events listed above that continue to meet the DLT requirements after the 7-day delay in study treatment will be considered DLT and the subject will be discontinued from study treatment. Any study treatment delay of greater than 7 days must be discussed with and approved by the masked Medical Monitor.

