2.6 Study Population

The study population will consist of men and women aged ≥ 18 years presenting with corneal endothelial dystrophy/ hypocellularity. Subjects will be recruited from a non-surgical population or post-operative cataract population (at least 3 months post-op). The intent is to enroll subjects with low ECD counts and endothelial cell images clearly quantitatable using specular microscopy imaging. Subjects included should not be expected to progress to transplantation within the study period of 3 months. The population is expected to include a mix of patients with corneal edema and those that do not yet have edema.

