5.1 Inclusion Criteria

- 1. Male or female, 18 years of age or older
- 2. Able and willing to provide informed consent

Trefoil Therapeutics, Inc.	Clinical Study Protocol TTHX-001
Confidential and Proprietary	Amendment 1.0: September 8, 2020

- 3. Fuchs Endothelial Corneal Dystrophy, pseudophakic bullous keratopathy, or endothelial dysfunction/ insufficiency due to surgical intervention diagnosed more than 6 months prior to Study Day 0 in the study eye
- 4. Intact anterior chamber anatomy (if posterior capsule is open or absent, absence of vitreous in the anterior chamber must be verified or enrollment approved by the Medical Monitor) in the study eye and no structural abnormalities that would make intracameral injection difficult
- 5. Able to obtain clear corneal endothelial cell (CEC) morphology and central CEC counts by specular microscopy from both eyes as determined by the central reading facility
- 6. Central endothelial cell count of < 2000 mm² in at least one eye as determined by the central reading facility during the screening period

Note: FECD patients with dense central guttae may not be countable and therefore, not eligible

- 7. Best Corrected Visual Acuity (BCVA) of at least 15 letters (per Early Treatment of Diabetic Retinopathy Study [ETDRS] testing) (approximately 20/400), in each eye
- 8. If female, are non-pregnant, non-lactating Subjects who are women of childbearing potential (WOCBP) must be using an acceptable method of birth control [e.g., an Intrauterine Contraceptive Device (IUCD), hormonal contraceptives, or double barrier method] starting at least 1 month prior to Study Day 0 and for the duration of the study. If a female subject is currently abstinent, they must agree to use a double barrier method of birth control before they become sexually active. Men who are sexually active with a woman of childbearing potential must agree to use a double barrier method.

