8. ASSESSMENT OF SAFETY

8.1 Adverse Events

Investigators will collect information related to adverse events (AEs) throughout this clinical trial. The terms and definitions are consistent with *Guidance for Industry and Investigators Safety Reporting Requirements for INDs and BA/BE Studies, FDA 2012.*

- All AEs occurring in all subjects following exposure to study treatment until 30 days after the last study treatment will be reported.
- AEs will be followed until at least the end of the study.
- AEs considered related to the study treatment by the Investigator (SARs) and SAEs will be followed until resolution, return to baseline, or stabilization (if resolution is not expected).

Changes in the subject's medical condition that occur prior to the first exposure to study treatment will be reported as medical history. At each post-treatment visit, subjects will be asked about any possible adverse events in a non-leading manner. An example of a non-leading method of eliciting AE information is "*Have there been any changes in your health since you were here last*?" Subjects should also be asked about the severity and/or persistence of any AEs that were ongoing at the time of their last visit.

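### Read literally, the >710 micron dose-limiting toxicity limb in 4.5.1 takes no account of Day 0 thickness, so an unchanged thick cornea would be recorded as a DLT (minor, but wrong as written)

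*Protocol*

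**What the plan says.** Section 4.5.1 defines the thickness criterion as ">710 micron corneal thickness or a 150 micron increase from baseline (Day 0 pretreatment"). It then prescribes three steps.

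- Hold: "If any subject experiences any of the events listed above, study treatment must be held for at least 7 days".
- Resume: besides continued eligibility, dosing may restart only once "all of the potential DLTs the subject experienced have decreased to a level that no longer meets the DLT requirements".
- Discontinue: a criterion still met after the 7-day delay "will be considered DLT and the subject will be discontinued from study treatment".

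Section 4.4.1 applies the DLT check to the Day 7, 14 and 21 injections, which may be given "as long as they remain eligible and have not experienced any dose limiting toxicity". It does not apply the check to Day 0.

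On who may enter, section 2.6 states: "The population is expected to include a mix of patients with corneal edema and those that do not yet have edema". Inclusion criterion 3 admits "Fuchs Endothelial Corneal Dystrophy, pseudophakic bullous keratopathy, or endothelial dysfunction/ insufficiency due to surgical intervention". Neither 5.1 nor 5.2 gives a limit in microns.

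**The concern.** The trial enrols patients whose disease can thicken the cornea. One limb of the thickness rule is an absolute level, and nothing at entry guarantees that an eye starts below that level. The rule can therefore be met by the condition the subject brought into the trial rather than by anything that happened after dosing.

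For such a subject, pre-existing disease would be labelled as toxicity and most of the planned dosing would be lost. The text can also be read as covering new findings only, so different sites (about 10 are planned) could handle the same eye differently.

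**Working it through.** There is no stated figure to reproduce. The check applies the decision rule as written.

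**Inputs**
- Criterion (4.5.1): thickness T > 710 microns, or T − B ≥ 150, where B is the Day 0 pretreatment value. A rise of exactly 150 is taken to count.
- Hold of at least 7 days, then recheck (4.5.1).
- Injections on Days 0, 7, 14 and 21 (4.4). The check governs the last three (4.4.1).
- Pachymetry is scheduled at Screening, on Day 0 before injection, and before the Day 7 and Day 14 injections (6.5).

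**Unchanged eye (T = B) above 710 microns, for example 730**
1. Day 0: no thickness criterion applies, so the eye is injected.
2. Day 7: 730 > 710, so the criterion is met and dosing is held.
3. Day 7 + 7 = Day 14: still 730 > 710, so it is recorded as a DLT and treatment is discontinued.
4. Injections given: 1/4 = 25%. Injections lost: 3/4 = 75%. Change in thickness: 0.

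To be dosed again, this eye would have to thin by at least 730 − 710 = 20 microns. An unchanged eye at 710 or below is never flagged and receives 4 of 4.

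**Smallest whole-micron rise that meets the rule** = min(150, 711 − B)

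| Day 0 thickness B | Rise that meets the rule |
|---|---|
| 560 or less | 150 |
| 650 | 61 |
| 700 | 11 |
| 710 | 1 |
| above 710 | none needed; already met |

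The rows at or below 710 show only how a ceiling works and are not an error. The last row is the defect.

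**Comparison with the other limbs.** Visual acuity and conjunctival hyperemia are defined as changes. The cell-count and IOP limbs are absolute, but 5.2 excludes a history of uveitis and of repeated elevated IOP, and the IOP limb also requires failure to respond to therapy. Only thickness combines an absolute limb with no corresponding entry criterion.

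**How many eyes.** The protocol gives no figure for the share p of enrolled eyes above 710 microns at Day 0. Purely as an illustration, with p assumed, the expected number among 71 subjects is 71p and the chance of at least one is 1 − (1 − p)^71:

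| Assumed p | Expected number | Chance of at least one |
|---|---|---|
| 0 | 0 | 0 |
| 1% | 0.71 | 51% |
| 2% | 1.42 | 76% |
| 5% | 3.55 | 97% |
| 10% | 7.1 | >99% |

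Nothing in the protocol favours one row over another. The entry requirements discussed below point towards the low end.

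**The case against.** The strongest reply has four parts.

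**Such eyes may never be enrolled.** Inclusion 5 requires clear endothelial images and central counts in both eyes, confirmed by the reading center. Section 2.6 seeks subjects not expected to need transplantation during the study. Exclusion 3 protects the view of the anterior chamber. Exclusion 17 lets the investigator turn away anyone at increased risk, and the Day 0 list ends with an eligibility check after pachymetry. This stands as a limit on frequency. None of these is a thickness limit, however, and exclusion 17 is discretionary. The public text of the injection procedure in 6.2 is incomplete, so a further pre-injection check cannot be ruled out.

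**An unchanged value is not an event that a subject experiences.** Section 8.1 adds: "Changes in the subject's medical condition that occur prior to the first exposure to study treatment will be reported as medical history". This makes a second reading possible but does not settle the matter. Section 8.1 governs adverse event reporting, and the resume and discontinue tests in 4.5.1 both turn on whether a level is still met. The masked Medical Monitor is contacted about management, but no power to waive discontinuation is stated.

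**A fixed ceiling is prudent in a first-in-human trial.** That is a fair clinical position. The text as it stands still does not deliver it, because the first injection may be given to an eye above the ceiling.

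**The trial-level consequences are slight.** This stands. A reader might infer that a false DLT would distort escalation or bias the Day 56 comparison, and the protocol does not support either inference. Section 4.6 has no DLT-count trigger. The unmasked Medical Monitor reviews all available data, which include the Day 0 thickness. Cohort review can take place once the last subject completes Day 7, before that subject could reach the Day 14 label. Section 5.3 expects subjects taken off treatment to stay on study for assessment.

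**Conclusion.** The point holds as a minor defect in a mandatory rule. Taken literally, 4.5.1 classifies an unchanged eye above 710 microns as a DLT and stops it after 1 of 4 injections. The effect is confined to the affected subject: a false toxicity label and three lost doses, with possible inconsistency between sites.

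The conclusion rests on reading the >710 micron limb as independent of Day 0, which is how the sentence is built, and on at least one such eye passing screening, which the protocol neither shows nor prevents. It would be wrong to infer that many subjects are affected, since the number is unknown and may be zero.

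**What to change.** Reword the thickness limb in 4.5.1, for example: *corneal thickness above 710 microns in an eye that was 710 microns or less at Day 0 before treatment; or an increase from Day 0 of 150 microns (or a smaller clinician-set increase for eyes above 710 microns at Day 0)*.

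Under this wording an unchanged 730 micron eye is not flagged on thickness and can receive 4 of 4 injections. Eyes at or below 710 microns are handled exactly as now.

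The cost is one sentence and no new assessment, since pachymetry is already scheduled and 6.4.8 requires one method within a subject. The downside is that the fixed ceiling is given up for the thickest corneas. With the full 150 micron allowance, a 730 micron eye would not be flagged until 730 + 150 = 880 microns, which is why clinicians may want a smaller increase for that group.

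If the sponsor intends 710 microns as an absolute safety ceiling, it should instead add a matching study-eye limit to 5.1, tested at Screening and confirmed on Day 0 before injection. A test only on Day 0 would leave some subjects randomized but not injected, because 6.1 randomizes before the additional baseline assessments. This option narrows eligibility slightly, and eyes admitted at 700 to 710 microns would still be flagged after a rise of only 11 down to 1 microns. It is therefore the second choice unless the ceiling itself is wanted.

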4.6 Stopping Rules

Stopping rules for the study will be the incidence of unacceptable toxicity. If, at any time, the safety profile is deemed unacceptable, study treatment will revert to the prior lower-dose level(s) deemed safe.

4.7 Investigational Product Accountability

In accordance with 21 CFR 312.61 and 21 CFR 312.62(a), the Investigator

- Will administer the drug only to subjects under the investigator's personal supervision or under the supervision of a subinvestigator responsible to the investigator,
- Shall not supply the investigational drug to any person not authorized under this part to receive it, and
- Will maintain adequate records of the disposition of the drug, including dates, quantity, and use by subjects

If the investigation is terminated, suspended, discontinued, or completed, the investigator shall return the unused supplies of the drug to the sponsor, or otherwise provide for disposition of the unused supplies of the drug under 21 CFR 312.59.

Trefoil Therapeutics, Inc.	Clinical Study Protocol TTHX-001
Confidential and Proprietary	Amendment 1.0: September 8, 2020

All thawed and partially used study treatment vials will be refrozen and stored. Unused and partially used study treatment vials will be returned to Trefoil (or designee) at the end of the Study Treatment Period.

4.8 Investigational Product Ordering and Resupply Request

Investigational sites will be provided with a subject-specific study treatment kit containing 5 vials at the time of randomization. In the event of loss or damage, the investigational site must contact the central study team and request replacement study treatment vial(s) for the specific subject. The drug depot will ship replacement masked study treatment vials corresponding with the subject's treatment assignment.

4.9 Maintenance of and Procedure for Breaking the Randomization Code

The randomization list will be maintained by the study team. An unmasked biostatistician (or designee) will provide the randomization list and masked Study Treatment Kit IDs to the study team.

In the event that unmasking a subject to treatment assignment is considered necessary prior to the database lock, the Investigator is instructed to contact the masked Medical Monitor to discuss the reasons for requesting unmasking. If the reason for requesting unmasking is for the management of adverse events or a decision to continue study treatment, the adverse events should be managed as medically appropriate and the subject should be discontinued from study treatment without unmasking. If unmasking is determined to be required, the masked Medical Monitor will contact the unmasked Medical Monitor and the masked Medical Monitor will communicate with the Investigator and reveal the subject's study treatment assignment.

4.10 Data to be Entered into the Database

Endothelial cell count/ density measured by the central reading facility is the primary efficacy endpoint for this study. The data generated by the central reading facility will be reconciled (Subject ID, date, time, timepoint) with the clinical database and the results will be uploaded into the database under a Quality and Data Transfer Specifications Agreement. Uploaded data will then be 100% quality checked (e.g.; sourced data verified) with the data at the central reading facility.

Other data and results generated by the investigational site will be data entered directly into the electronic data capture (EDC) system. All data in the EDC will be monitored and critical variables will be 100% source data verified.

5. SELECTION AND WITHDRAWAL OF SUBJECTS

Patients will be primarily selected on the basis of diagnosis of Corneal Endothelial Dystrophy and corneal endothelial cell (CEC) hypocellularity. Eligibility may be based on the pathology noted in one or both eyes. If both eyes meet ocular eligibility criteria, the eye with the lower CEC count will be designated as the study eye (SE); if only 1 eye meets the eligibility criteria, it will be the SE.

5.1 Inclusion Criteria

- 1. Male or female, 18 years of age or older
- 2. Able and willing to provide informed consent

Trefoil Therapeutics, Inc.	Clinical Study Protocol TTHX-001
Confidential and Proprietary	Amendment 1.0: September 8, 2020

- 3. Fuchs Endothelial Corneal Dystrophy, pseudophakic bullous keratopathy, or endothelial dysfunction/ insufficiency due to surgical intervention diagnosed more than 6 months prior to Study Day 0 in the study eye
- 4. Intact anterior chamber anatomy (if posterior capsule is open or absent, absence of vitreous in the anterior chamber must be verified or enrollment approved by the Medical Monitor) in the study eye and no structural abnormalities that would make intracameral injection difficult
- 5. Able to obtain clear corneal endothelial cell (CEC) morphology and central CEC counts by specular microscopy from both eyes as determined by the central reading facility
- 6. Central endothelial cell count of < 2000 mm² in at least one eye as determined by the central reading facility during the screening period

Note: FECD patients with dense central guttae may not be countable and therefore, not eligible

- 7. Best Corrected Visual Acuity (BCVA) of at least 15 letters (per Early Treatment of Diabetic Retinopathy Study [ETDRS] testing) (approximately 20/400), in each eye
- 8. If female, are non-pregnant, non-lactating Subjects who are women of childbearing potential (WOCBP) must be using an acceptable method of birth control [e.g., an Intrauterine Contraceptive Device (IUCD), hormonal contraceptives, or double barrier method] starting at least 1 month prior to Study Day 0 and for the duration of the study. If a female subject is currently abstinent, they must agree to use a double barrier method of birth control before they become sexually active. Men who are sexually active with a woman of childbearing potential must agree to use a double barrier method.

